9.3 Other PK analyses/variables

Not applicable.

10 SAFETY ANALYSES

The SS will be used to summarize and analyze all safety variables. In case of dosing administration error, summaries and analyses using the SS will be conducted according to actual treatment administered according to the rule described in Section 3.6. Safety data will be summarized for each treatment group and the PSL total group.

10.1 Extent of exposure

Extent of exposure will be based on the SS. The date of first dose is reported on First Administration of Study Medication CRF. The date of last dose is reported on the Study Termination CRF. If the date of last dose is missing due to lost to follow-up, the date of the last scheduled or unscheduled visit will be used.

The duration of study drug exposure for the Treatment Period will be calculated as the date of the last dose of study drug during the 16-week Treatment Period minus the date of first dose of

study drug plus 1 day. Date of the last dose of study drug during the 16-week Treatment Period is defined as the overall study last dose date or the end date of the 16-week Treatment Period, whichever is earlier.

Exposure (in days) will be summarized as a continuous variable for the 16-week treatment period. The number and percentage of subjects with the following categories of durations of exposure for the Treatment Period will also be summarized: >0 weeks, >=4 weeks, >=8 weeks, >=12 weeks, >=16 weeks.

10.2 Adverse events

Adverse events are recorded on the AE CRF as they occur, from the time informed consent is granted until study completion or study termination (end of the SFU period 30 days after the last IMP intake). All AEs will be coded using the latest available version of MedDRA.

A treatment-emergent adverse event (TEAE) is defined as any event not present prior to the initiation of the first dose of study treatment or any unresolved event already present before initiation of the first dose that worsens in intensity following exposure to the treatment. The number and percentage of subjects who experience TEAEs at any time during the study will be summarized by SOC and PT. The following tabular summaries will be presented for the SS:

- Incidence of TEAEs during the Treatment Period – Overview. Of note, the corresponding table is required for data transparency reporting.
- Incidence of TEAEs by period (Treatment Period, Titration and Stabilization Period, Maintenance Period, Conversion Period, and Taper and SFU Period)
- Incidence of Serious TEAEs by period (Treatment Period, Titration and Stabilization Period, and Maintenance Period)
- Incidence of TEAEs leading to discontinuation by period (Treatment Period, Titration and Stabilization Period, and Maintenance Period)
- Incidence of TEAEs leading to dose reduction during the Stabilization Period

The following will be presented for TEAEs during the overall Treatment Period:

- Subject numbers for TEAEs
- Incidence of TEAEs occurring in at least 5% of subjects in any treatment group
- Incidence of TEAEs occurring in at least 2% of subjects in any PSL group and greater than placebo group
- Incidence of TEAEs by Relationship
- Incidence of TEAEs by Maximum Intensity
- Incidence of SAEs by Relationship. Of note, the corresponding table is required for data transparency reporting.
- Incidence of Fatal TEAEs by Relationship. Of note, the corresponding table is required for data transparency reporting.

- Incidence of Non-Serious TEAEs above the threshold of 5% of subjects in any treatment group. Of note, the corresponding table is required for data transparency reporting.
- Summary of the duration in days per event for the following TEAEs: somnolence, dizziness, fatigue, irritability and headache. In this analysis, if an AE is ongoing, the duration will be calculated till the date of final contact.

Summaries will be presented based on standard Sponsor AE table formats and considering formats used for the PSL program.

Where dates are missing or partially missing, AEs will be assumed to be treatment-emergent, unless there is unmistakable evidence (through comparison of partial dates, see Section 4.2) to suggest that the AE started prior to the first dose of study treatment. Summary tables will contain counts of subjects, percentages of subjects in parentheses and the number of events where applicable. A subject who has multiple events in the same MedDRA category (SOC or PT) will be counted only once in the subject count for that category, however all events will be included in the event count for the category. In summaries including relationship to study treatment, the following relationships will be summarized: 'Not related', 'Related'. A subject may be counted more than once according to the relationship to study treatment. Events with missing relationship will be considered as 'Related' to the last given study product for summary purposes but recorded as missing in the listings. In summaries of the maximum intensity, the following intensity categories will be summarized: 'Mild', 'Moderate', 'Severe'. Subjects who experience the same event multiple times, with differing severities, will be included in the most severe category. Events with missing intensity will be considered as 'Severe' events for summary purposes but recorded as missing in the listings. The main reasons for treatment discontinuation will be listed by subject. The daily dose of study medication corresponding to the AE onset date will be included in the listing. Daily dose will be derived from 'Study Medication Administration' CRF.

Adverse event summaries will be ordered in terms of decreasing frequency for SOC, and PT within SOC, within the PSL total group column.

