### **4.2.2 Other safety variables**

Other safety variables are as follows:

- Incidence of TEAEs reported by the subject and/or caregiver or observed by the Investigator during the following periods: 16-week Treatment Period, 12-week Maintenance Period, 4-week Titration/Stabilization Period, and 3-week Taper Period
- Number of and reason for subjects requiring premature tapering due to TEAEs
- Number of and reason for subjects requiring a dose reduction during the Stabilization Period due to TEAEs
- Incidence of treatment-emergent SAEs during the following periods: 16-week Treatment Period, 12-week Maintenance Period, 4-week Titration/Stabilization Period
- Changes in clinical laboratory test parameters (including hematology, blood chemistry, and urinalysis)
- Changes in vital sign parameters (including pulse rate, SBP, DBP, and respiratory rate)
- Changes in 12-lead ECG parameters
- Physical examination (including body weight) and neurological examination findings
- Changes in Psychiatric and Mental Status exam
- Occurrence of valvular abnormalities or pericardial effusion changes or other significant abnormalities as identified by 2-dimensional Doppler echocardiogram at each assessment by central reader
- Changes in withdrawal symptoms using Clinical Institute Withdrawal Assessment-Benzodiazepines (CIWA-B) from the end of the 16-week Treatment Period (Visit 7) to the end of the Taper Period (Visit 8) and the end of the SFU Period (Visit 9 [30 days after the last IMP intake])

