#### Safety Follow-up Period (1 month)

Safety follow up for all subjects not entering the OLE will consist of 1 required visit, 30 days after the last IMP intake (Week 23 or sooner in case of early discontinuation), including an echocardiogram. An additional follow-up echocardiogram will be performed at 6 months ( $\pm 1$  month) after the last IMP intake only for subjects exposed to IMP for more than 3 weeks.

*For subjects continuing to the OLE study:*

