2.3.2 Other safety variables

Other safety variables are as follows:

- Incidence of TEAEs reported by the subject and/or caregiver or observed by the Investigator during the following periods: 16-week Treatment Period, 12-week Maintenance Period, 4-week Titration/Stabilization Period, and 3-week Taper Period
- Number of and reason for subjects requiring premature tapering due to TEAEs
- Number of and reason for subjects requiring a dose reduction during the Stabilization Period due to TEAEs
- Incidence of treatment-emergent SAEs during the following periods: 16-week Treatment Period, 12-week Maintenance Period, 4-week Titration/Stabilization Period
- Changes in clinical laboratory test parameters (including hematology, blood chemistry, and urinalysis)
- Changes in vital sign parameters (including pulse rate, systolic BP, diastolic BP, and respiratory rate)
- Changes in 12-lead ECG parameters

- Physical examination (including body weight) and neurological examination findings
- Changes in Psychiatric and Mental Status
- Occurrence of valvular abnormalities or pericardial effusion changes or other significant abnormalities as identified by 2-dimensional Doppler echocardiogram at each assessment by central reader
- Changes in withdrawal symptoms using Clinical Institute Withdrawal Assessment-Benzodiazepines (CIWA-B) from the End of Treatment Visit (Visit 7) to end of the Taper Period (Visit 8) and end of the SFU Period (Visit 9 [30 days after the last IMP intake]).

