Taper and Safety Follow-up	The date of the day after Visit 7/EDV or the date of day after Visit 8 if the subject tapered after conversion	The date of final contact.	Subjects who withdraw from the study or decide not to participate in the OLE study will be tapered off the IMP during a 3-week period followed by a 1-week drug-free period. A SFU visit will be performed 30 days after the last IMP intake.

OLE=open-label extension; SFU=Safety Follow Up

* Only seizure data prior to and on the date of last dose of study medication will be included in the analysis.

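### TEAE incidence is defined for a Taper Period, but the SAP tabulates it only over taper and safety follow-up combined and does not declare the change

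*SAP*

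**What the plan says.** Protocol 4.2.2 lists TEAE incidence by period among the other safety variables, and the periods end with "4-week Titration/Stabilization Period, and 3-week Taper Period". SAP 2.3.2 repeats the variable for the "16-week Treatment Period, 12-week Maintenance Period, 4-week Titration/Stabilization Period, and 3-week Taper Period". This is current SAP text, not superseded wording.

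SAP Table 3-1 has no row for the taper alone. Its last row joins taper and safety follow-up. The start is "The date of the day after Visit 7/EDV or the date of day after Visit 8 if the subject tapered after conversion"; the end is "The date of final contact". The same row describes subjects as "tapered off the IMP during a 3-week period followed by a 1-week drug-free period", with the follow-up visit after that. Protocol 5.1 places that visit "30 days after the last IMP intake (Week 23 or sooner in case of early discontinuation").

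SAP 10.2 then plans "Incidence of TEAEs by period (Treatment Period, Titration and Stabilization Period, Maintenance Period, Conversion Period, and Taper and SFU Period"). The tables give counts and percentages of subjects, not exposure-adjusted rates. SAP 3.9, which lists changes to protocol-defined analyses, does not mention the taper period.

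The documents are also not consistent on the length of the taper. It is 3 weeks in Protocol 4.2.2 and 7.2.2 and in SAP 2.3.2. In Protocol 5.1 and SAP 2.5.1 it is a 4-week period made up of 3 weeks of dose reduction and 1 drug-free week, and footnote a of Protocol Table 5-1 describes the same structure.

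**The concern.** A programmer who follows the SAP exactly will not produce a safety variable that the SAP itself defines. The nearest table spans dose reduction, the drug-free week and the rest of follow-up. An event in the first week of taper and an event four weeks after the last tablet count alike.

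This matters because a withdrawal syndrome is a question for this drug. Protocol 2.3.1 reports that new AEs, mainly headache and sleep disturbance, appeared after dosing stopped in Phase 1 and may indicate withdrawal. Protocol 7.2.2 and 11.7.8 ask sites to monitor withdrawal-related AEs during the taper. A reader of the study report would want to know, by arm, whether events began while the dose was falling or after it reached zero. The planned table cannot answer that.

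**Working it through.** **Inputs.** From Protocol Table 5-1: Visit 1 = Day -28, Visit 7 = Day 112, Visit 8 (taper) = Day 140, Visit 9 = Day 161 with a window of ±7 days. The taper is 21 days of dosing plus 7 drug-free days. Final contact is taken as Visit 9, where Protocol 8.4 places study termination for subjects not entering the extension. The SAP does not itself tie the two together.

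**Check of the calendar against the plan's own figures.** Total duration = (161 + 28)/7 = 27 weeks. Maximum exposure = 16 + 3 = 19 weeks. Both match Protocol 5.1.1.

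**Window lengths.**
- Combined period in SAP Table 3-1: Day 113 to Day 161 = 161 - 113 + 1 = 49 days. With Visit 9 a week early or late: 42 to 56 days. With follow-up exactly 30 days after a last dose on Day 133: 163 - 113 + 1 = 51 days.
- Taper dosing only: Day 113 to Day 133 = 21 days. Ratio 49/21 = 2.33; the 28 days after dosing are 28/49 = 57% of the window.
- Taper with the drug-free week: Day 113 to Day 140 = 28 days. Ratio 49/28 = 1.75; the 21 days beyond it are 21/49 = 43% of the window.

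**Effect on the contrast between arms.** The documents give no event rates, so this is an illustration only. Assume a constant background hazard giving 10% incidence in 21 days, so the probability of no event over d days is 0.9^(d/21). Placebo incidence is then 10.0% over 21 days, 1 - 0.9^(28/21) = 13.1% over the 28 days after the last dose, and 1 - 0.9^(49/21) = 21.8% over 49 days. Let PSL double the hazard in one phase only.

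- Doubling during the 21 dosing days. Taper table: 1 - 0.9^2 = 19.0% vs 10.0%, ratio 1.90, difference 9.0 points. Combined table: 1 - 0.9^(2 + 28/21) = 29.6% vs 21.8%, ratio 1.36, difference 7.8 points.
- Doubling during the 28 days after the last dose. Taper table: 10.0% vs 10.0%, ratio 1.00. Follow-up table: 1 - 0.9^(56/21) = 24.5% vs 13.1%, ratio 1.87. Combined table: 1 - 0.9^(1 + 56/21) = 32.0% vs 21.8%, ratio 1.47, difference 10.2 points.

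Compared with a 21-day taper table, the combined table weakens the contrast in the first case and reveals it in the second. In both cases the split tables show which phase carries the excess, and the combined table does not.

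**The case against.** A reader might infer that the long window dilutes any withdrawal signal. The documents do not support that. Protocol 2.3.1 places the Phase 1 events after discontinuation, where a 21-day taper table alone could show nothing and the combined window would pick them up. With a fixed denominator, a cumulative percentage cannot fall when the window is lengthened, and SAP 10.2 plans no between-arm test or ratio that could be biased. This part of the objection stands in full.

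Nor is the timing information lost. The AE listing carries the daily dose at onset (SAP 10.2), and relative days after the last dose are counted from that dose (SAP 3.2.2.1). Withdrawal has its own instrument, the CIWA-B, at Visits 7, 8 and 9, with a summary by visit (SAP 10.4.4.5). This limits the harm but does not close the gap. Listings give no incidence by arm. No CIWA-B visit is scheduled between the start of taper at Visit 7 and Visit 8, one week after the last intake.

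The 49 days is nominal, since Protocol 5.1 and 7.2.2 allow faster or slower tapers. Which shorter window is the right comparator depends on the unresolved 3-week or 4-week description. Both caveats stand. Neither makes the combined period equal to the defined one.

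**Conclusion.** The mismatch holds. Protocol 4.2.2 and SAP 2.3.2 define a Taper Period incidence. SAP Table 3-1 and 10.2 replace it with a period nominally 1.75 to 2.33 times as long, depending on whether the drug-free week belongs to the taper, and SAP 3.9 does not say so. The defined figure is never tabulated, and timing relative to the last dose cannot be read by arm.

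The size rests on the nominal visit days and on final contact falling at Visit 9. No direction is claimed for the effect on the PSL-placebo contrast; that depends on when withdrawal events start, which the documents do not settle.

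Severity is minor. The variable is descriptive and sits among the other safety variables. No primary safety variable and no efficacy conclusion changes. Protocol 2.3.1 also describes the earlier events as mild and transient.

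**What to change.** 1. Reconcile the 3-week and 4-week descriptions of the Taper Period for analysis purposes, and state in SAP Table 3-1 whether the drug-free week belongs to it.
2. Split the last row of SAP Table 3-1 into Taper and post-taper Safety Follow-Up, with the boundary taken from the last-dose and visit dates already collected.
3. In SAP 10.2, tabulate TEAEs for each part separately. The combined table can stay as an addition.
4. If only the combined table is wanted, amend SAP 2.3.2 to match it and list the change in SAP 3.9.

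The cost is SAP wording and one extra descriptive table (two if the combined table is also kept). No new data are needed.

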## **13.4 Planned safety and other analyses**

### **13.4.1 Safety analyses**

Adverse events will be coded using the Medical Dictionary for Regulatory Activities (MedDRA®). Adverse events will be summarized by MedDRA System Organ Class and Preferred Term. The incidence of SAEs, AEs leading to premature discontinuation or dose tapering, and related AEs, and the incidence of AEs by maximum intensity, will also be summarized.

Laboratory values, ECG data (heart rate, PR interval, QRS duration, QT interval, QTcB or QTcF, and Investigator's conclusion on ECG profile) and arrhythmias, vital signs, weight, and changes from Baseline in these measures will be summarized by period, visit, and treatment group. Possibly clinically significant treatment-emergent abnormalities for laboratory values, vital signs, and weight will be listed and summarized by period and visit for each treatment group.

Electrocardiogram abnormalities as well as physical and neurological abnormalities will also be listed by period and visit. Quantitative safety parameters will be summarized descriptively by time point and treatment group. Categorical safety summaries will provide the number and percentage of subjects within each summarized category.

Doppler echocardiogram results at Baseline and during and after treatment, and changes from Baseline, will be listed and descriptively summarized.

All C-SSRS data obtained at Baseline and subsequent visits will be reported as a listing ordered by subject and visit. Psychiatric and Mental Status assessment and CIWA-B data will also be included using listings.

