2.3 Safety variables

2.3.1 Primary safety variables

The safety variables are as follows:

- Incidence of TEAEs reported by the subject and/or caregiver or observed by the Investigator during the entire study
- Incidence of TEAEs leading to study withdrawal
- Incidence of treatment-emergent serious adverse events (SAEs) during the entire study

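### SAP 10.2 plans no table of treatment-emergent SAEs over the entire study, although this is a primary safety variable

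*SAP*

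**What the plan says.** **The variable.** Among the primary safety variables, SAP 2.3.1 lists "Incidence of treatment-emergent serious adverse events (SAEs) during the entire study". Protocol 4.2.1 has the same variable. The analysis section of the protocol (13.4.1) calls for a summary of SAE incidence and names no period: "The incidence of SAEs, AEs leading to premature discontinuation or dose tapering, and related AEs".

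A separate, non-primary variable in SAP 2.3.2 (and Protocol 4.2.2) covers SAEs by period: "Incidence of treatment-emergent SAEs during the following periods: 16-week Treatment Period, 12-week Maintenance Period, 4-week Titration/Stabilization Period".

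**The planned tables.** SAP 10.2 lists, for serious events, "Incidence of Serious TEAEs by period (Treatment Period, Titration and Stabilization Period, and Maintenance Period". For all TEAEs the corresponding table has a longer list of periods: "Incidence of TEAEs by period (Treatment Period, Titration and Stabilization Period, Maintenance Period, Conversion Period, and Taper and SFU Period".

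A second group of tables is introduced by "The following will be presented for TEAEs during the overall Treatment Period". It contains SAEs by relationship and "Incidence of Fatal TEAEs by Relationship". The TEAE overview table is likewise for the Treatment Period.

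One general sentence has no period limit: "The number and percentage of subjects who experience TEAEs at any time during the study will be summarized by SOC and PT".

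**The concern.** The three periods in the serious-TEAE table are those of the secondary-tier variable in SAP 2.3.2. That variable has a table; the primary one does not. SAP 2.3.1 still carries the primary variable, so the SAP disagrees with itself.

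The omitted weeks are ones the protocol treats as a time to watch. Protocol 2.3.1 reports AEs after stopping PSL in Phase 1 that pointed to a possible withdrawal syndrome, although it describes them as mild and transient. Protocol 7.2.2 and 11.7.8 require monitoring for withdrawal symptoms and for seizures during taper. Table 11-1 lists status epilepticus and cluster seizures among the anticipated SAEs. Placebo subjects who enter the Conversion Period receive PSL for the first time then. For early discontinuers the Treatment Period closes at the early discontinuation visit, so a serious event during their taper falls outside every serious-TEAE table.

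A reader who wanted the incidence of late serious or fatal events by arm would have to count them by hand from the listings.

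**Working it through.** The plan states no figure to reproduce. The check matches the variable to the planned outputs and then counts the scheduled days left out.

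**Step 1. Does any planned output give SAE incidence over the entire study?**

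| Output | Window | Separates serious events? |
|---|---|---|
| Serious TEAEs by period (SAP 10.2) | Treatment, Titration/Stabilization, Maintenance | Yes |
| SAEs by relationship; fatal TEAEs by relationship (SAP 10.2) | Treatment Period | Yes |
| TEAE overview (SAP 10.2) | Treatment Period | Not needed: the window already falls short |
| All TEAEs by period (SAP 10.2) | Adds Conversion and Taper/SFU | No |
| TEAEs at any time, by SOC and PT (SAP 10.2) | Entire study | No |
| Discontinuations due to AE (SAP 5.1) | No period limit | Yes, but only subjects who discontinued because of an AE |
| AE listings (SAP 3.1, 10.2) | All data | Not an incidence by arm |

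No row combines the entire-study window with a count of all subjects who had a serious event.

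**Step 2. Where does the Treatment Period end?** SAP 3.2.2.2 ends it at Visit 7 or the early discontinuation visit, and at last contact only if neither took place. For a subject with either visit, later events are outside it.

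**Step 3. What is the entire study?** Protocol 5.1.1 and SAP 2.5.2 define the end of the study by the last safety follow-up visit, 30 days after the last IMP intake. SAP 10.2 has AEs recorded to the same point. Conversion, taper and follow-up are therefore inside it.

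**Step 4. Is the narrower window a documented change?** SAP 3.9 lists the changes from the protocol, and this is not among them.

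**Step 5. How much scheduled time is left out?** Inputs are the day numbers in Protocol Table 5-1 (Visit 7 = 112, Visit 8 for conversion = 133, safety follow-up = 161) and the 3-week taper on IMP in Protocol 5.1.

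Completers who taper:
- taper on IMP: 3 × 7 = 21 days, ending on day 112 + 21 = 133
- drug-free days to follow-up: 161 − 133 = 28
- total omitted: 21 + 28 = 49 days; 49/161 = 0.304 (30%), made up of 21/161 = 0.130 (13%) and 28/161 = 0.174 (17%)

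Completers who convert:
- omitted: 133 − 112 = 21 days; 21/133 = 0.158 (16%)

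Time on IMP omitted in either group: 21/133 = 0.158. As a cross-check, SAP 2.5.2 gives a maximum PSL exposure of 19 weeks; 19 − 16 = 3 weeks and 3/19 = 0.158. The cross-check applies to subjects randomized to PSL. For placebo subjects who convert, all PSL exposure in this study lies after Visit 7.

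**The case against.** **The requirement may still be in force through SAP 1.** SAP 1 falls back on the protocol where the SAP does not specify otherwise. The three-period bullet implements a different variable, and SAP 3.9 removes nothing, so the entire-study summary could be read as still required. Sponsor-standard AE table formats, which SAP 10.2 invokes but does not show, might also carry a serious subset. Neither argument closes the gap. SAP 10.2 does specify the periods for serious events, and nothing in the text promises a serious subset outside them. At best the table is required but unlisted, and it still needs to be listed.

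**The fix asks for more than the variable does.** A single entire-study count would satisfy Protocol 4.2.1. Fatal events are not a separate safety variable, and neither document asks for SAEs by Conversion or Taper/SFU. This is correct. Those rows and columns are additions that help the reader, at little cost.

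**The window is not settled.** SAE reporting continues until the 6-month echocardiogram (Protocol 5.1.1 and 11.1.2.3). The documents state this as additional to an end of study at safety follow-up, and SAP 10.2 stops AE recording there, so first dose to end of follow-up is the window that fits their own definitions. It should be written down, because the table would not cover the later SAE reporting.

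**The effect is modest.** The day shares are not event shares and describe completers on nominal days. Only a descriptive output is affected. Both points stand and limit how serious this is.

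**Conclusion.** The point holds. Followed as written, SAP 10.2 produces no table for one of the three primary safety variables, and the tables it does plan for serious and fatal events stop at the end of the Treatment Period. The omission is undocumented and should be corrected.

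The size is known only as calendar time: 30% of the scheduled days for completers who taper and 16% for those who convert. This assumes nominal visit days, before visit windows and permitted changes in taper length. The documents give no event rates for these periods, so the number of serious events affected cannot be estimated. No share is given for early discontinuers, because their discontinuation day and taper length vary.

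Efficacy inference is untouched. The events remain in the listings, with the daily dose at onset, and in the all-TEAE counts.

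**What to change.** In SAP 10.2, add one table of serious TEAEs for the entire study, defined as first dose to the end of safety follow-up. Present it by treatment group and PSL total, with a fatal row and with Conversion and Taper/SFU shown as periods.

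Optionally, say where events in placebo subjects are counted once they receive PSL in the Conversion Period; the SAP is silent on this. In the new table and in the any-time TEAE summary, events beginning on or after the first Conversion dose in these subjects could be shown separately from Placebo.

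The cost is one descriptive table, or 1 × 3 = 3 (overall, Japan, non-Japan) under the SAP 16 repeat rule. It uses data already collected and changes no endpoint or test.
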